## 2.6 Clinical Data

Based on the efficacy and safety data from the key clinical, Table below (Table 3) provides the recommended GZR/EBR treatment regimen and duration based on the patient population and genotype in hepatitis C virus (HCV) mono-infected and HCV/HIV-1 co-infected patients with or without cirrhosis.

**Table 3 : Recommended Dosage Regimens and Durations for EBR/GZR for Treatment of Chronic Hepatitis C Infection in Patients with or without Cirrhosis**

HCV genotype	Treatment and duration
1a	ZEPATIER for 12 weeks  ZEPATIER for 16 weeks plus ribavirin A should be considered in patients with baseline HCV RNA level >800,000 IU/ml and/or the presence of specific NS5A polymorphisms causing at least a 5-fold reduction in activity of elbasvir to minimise the risk of treatment failure (see section 5.1).
1b	ZEPATIER for 12 weeks
4	ZEPATIER for 12 weeks  ZEPATIER for 16 weeks plus ribavirin A should be considered in patients with baseline HCV RNA level >800,000 IU/ml to minimise the risk of treatment failure (see section 5.1).

A In the clinical studies, the dose of ribavirin was weight-based (< 66 kg = 800 mg/day, 66 to 80 kg = 1,000 mg/day, 81 to 105 kg = 1,200 mg/day, > 105 kg = 1,400 mg/day) administered in two divided doses with food.

In case a dose is missed and it is within 16 hours of the time GZR/EBR is usually taken, the patient should be instructed to take GZR/EBR as soon as possible and then take the next dose of GZR/EBR at the usual time. If more than 16 hours have passed since GZR/EBR is usually taken, then the patient should be instructed that the missed dose should NOT be taken and to take the next dose per the usual dosing schedule. Patients should be instructed not to take a double dose.

If GZR/EBR is co-administered with ribavirin or sofosbuvir, the information for ribavirin or sofosbuvir with regard to contraception, pregnancy testing, pregnancy, breastfeeding, and fertility also applies to this combination regimen (refer to the prescribing information of the co-administered medicinal product for additional information).

## **2.7 Recent clinical trials with 8 weeks of treatment containing DAAs**

The protease inhibitor ABT-450 with ritonavir (ABT-450/r), the nonnucleoside polymerase inhibitor ABT-333, and ribavirin showed efficacy against the hepatitis C virus (HCV) in a pilot study involving patients with HCV genotype 1 infection. The addition of another potent agent, the NS5A inhibitor ABT-267, may improve efficacy, especially in difficult-to-treat patients. This study was designed to evaluate multiple regimens of direct-acting antiviral agents and ribavirin in patients with HCV genotype 1 infection without cirrhosis who had not received therapy previously or who had no response to prior therapy with pegylated interferon and ribavirin.

In this phase 2b study of interferon-free antiviral regimens, the treatment regimens were associated with rates of sustained virologic response at 24 weeks after treatment that ranged from 83 to 100%. Among previously untreated patients, the rate of treatment failure was lower among those receiving three direct acting agents plus ribavirin for 12 weeks than among those who received the same regimen for only 8 weeks and among those who received fewer agents; extending the treatment to 24 weeks offered no further benefit. The rate of sustained virologic response at 24 weeks after treatment was 88% in the subgroup that received 8 weeks of therapy and 95% in the subgroup that received 12 weeks of therapy (difference between 8-week and 12-week subgroups, -7 percentage points; 95% confidence interval, -19 to 5;  $P = 0.24$ ). The higher number of relapses among patients in the 8-week treatment group (in 10 of 80 patients, vs. in 1 of 79 patients in the 12-week treatment group) and the absence of resistance-associated variants in most patients who had a relapse in the 8-week treatment group suggest that 8 weeks of treatment might not be sufficient to eradicate the susceptible HCV population in these patients.

Treatment durations longer than 8 weeks were not associated with a less favorable safety profile (21).

In a phase 3 trial involving previously untreated patients with HCV genotype 1 infection without cirrhosis to explore the feasibility of shortening the treatment duration. It was assessed the single-tablet regimen of ledipasvir–sofosbuvir administered for 8 weeks, with or without ribavirin (Ribasphere, Kadmon Pharmaceuticals), as compared with ledipasvir–sofosbuvir alone administered for 12 weeks.

In conclusion of this phase 3 trial, 8 weeks of treatment with a single-tablet regimen of ledipasvir–sofosbuvir resulted in a high rate of sustained virologic response among previously untreated patients with HCV genotype 1 infection without cirrhosis. Indeed, the SVR was 94 % (95% confidence interval [CI], 90 to 97). This results show that ribavirin worsens the treatment burden without enhancing efficacy. A 12 weeks duration of treatment with ledipasvir–sofosbuvir was not more effective than 8 weeks of treatment. The uniformly high rates of response in all the patient subgroups suggest the efficacy of this regimen across a broad range of previously untreated patients with HCV genotype 1 infection without cirrhosis. The 8-week regimen of ledipasvir–sofosbuvir has not been evaluated in patients with cirrhosis (12).

In a phase 2 study of treatment-naïve noncirrhotic patients treated by Sofosbuvir With Velpatasvir in Genotype 1 to 6 Hepatitis C Virus Infection, Rates of SVR were lower with 8 weeks versus 12 weeks of treatment in patients with HCV genotype 1 or 2 infection. More particularly for genotype 1, SVR was 85% (95% CI). The small sample size and limited number of virologic failures in each treatment group precluded analysis of the association between viral load and virologic failure. The high SVR rates achieved with 12 weeks of treatment, even in patients with pretreatment RAVs, may indicate that the 12-week regimen is more efficacious for patients with negative predictors, such as baseline resistance (22).

High efficacy was also demonstrated in treatment-naïve, non-cirrhotic (F0-F3) GT1b infected patients in 8 weeks of treatment by EBR/GZR.

Indeed, in the Protocol 035/C-WORTHY trial (Cf ANNEXE n°1), treatment-naïve subjects with genotype 1b CHC without cirrhosis were treated with GZR + EBR with or without RBV for 8 weeks. In subjects treated with GZR + EBR without RBV, the subjects had a median age of 56 years (range: 28 to 71); 42% of the subjects were male; 81% were White; 19% were Black or African American; 3% were Hispanic or Latino; mean body mass index was 28 kg/m^2; 87% had baseline HCV RNA levels greater than 800,000 IU/mL; and 90% had non-C/C IL28B alleles (CT or TT). By liver biopsy or non-invasive tests, all were non-cirrhotic and 94% (29/31) had METAVIR scores of F0-F2 and the other 2 subjects had a METAVIR score of F3.

Overall SVR was achieved in 94% (29/31) in treatment-naïve subjects with genotype 1b without cirrhosis who received GZR + EBR for 8 weeks. Two of the thirty-one subjects did not achieve SVR due to relapse. SVR was achieved in 97% (28/29) of subjects with METAVIR scores of F0-F2 and 50% (1/2) subjects with METAVIR score of F3. The addition of RBV was not shown to improve the treatment outcomes observed with GZR + EBR (23,24).

A summary of this studies are presented in the table 4 :

**Table 4 : Summary of treatment studies of genotype 1 patients during 8 weeks and without cirrhosis**

Treatment combination	SVR Genotype 1b	SVR Genotype 1	Comments
Elbasvir + Grazoprevir	97% (29/31)	NA	F0-F2 patients
3D Abbvie +/- RBV	NA	88% (70/80)	F2- F3 patients
Sofosbuvir + Ledipasvir	98% (42/43)	94% (202/215) *	F0-F3 patients * F3 (19%); Genotype 1a : 80%; Genotype 1b : 20%
Sofosbuvir + Velpatasvir(100mg)	NA	84% (51/60)	F0-F3 patients

Results of these studies suggest that 8 weeks of treatment with EBR/GZR combination might be sufficient to eradicate the susceptible HCV population in treatment-naïve, non-severe fibrosis (F0-F2) GT1b infected patients (12,21–25).

## 2.8 Rationale for the Trial

Details regarding specific benefits and risks for subjects participating in this clinical trial may be found in the accompanying Investigators Brochure (IB) and Informed Consent documents.

### 2.8.1 Overview of Efficacy Endpoints

The primary measurement for efficacy in this study is the plasma HCV RNA level. Long term suppression of HCV RNA, typically reported as Sustained Virologic Response (SVR), has been associated with improved outcomes in subjects with chronic hepatitis C infection as measured by biochemical and histological remission of liver disease. Though long term outcome data are limited, most available data suggest that SVR following antiviral therapy reduces the risk of progression to cirrhosis and may prevent the development of severe liver complications and improve survival (26).

The primary evaluation of efficacy in this trial is based on SVR12 (Sustained Virologic Response 12 weeks after the end of all study therapy). The primary endpoint used in Phase III trials for all currently approved anti-HCV therapy has been based on SVR24 (Sustained Virologic Response 24 weeks after the end of all study therapy). However, a high degree of concordance has been observed between SVR12 and SVR24 (27), and SVR12 is increasingly being used as the primary endpoint in more recent Phase III trials. Therefore, it is appropriate to use SVR12 as the primary efficacy endpoint in this trial; SVR24 will be a key secondary efficacy endpoint.

Other secondary evaluations of efficacy are based on SVR4 (Sustained Virologic Response 4 weeks after the end of all study therapy), HCV RNA measurements at Week 2, Week 4, and end of treatment visit (Week 8).

### **2.8.2 Measurements of HCV RNA**

HCV-RNA levels in plasma will be measured using the Roche COBAS™ Taqman™ HCV Test, v2.0 for use with the High Pure system or ABBOTT Amplification Reagent Real Time kit HCV on blood samples drawn from each subject at various time points, prior to, during, and after dosing, as indicated in the Study Flow Chart (Section 7). Samples will be collected and processed as per provided instructions.

Results from samples collected at the screening visit are used to determine eligibility. Samples collected at other time points are used for efficacy analyses. They are also used to identify subjects who meet virologic failure criteria.

The Roche COBAS™ Taqman™ HCV Test, v2.0® for use with the High Pure system assay has a lower limit of detection and quantitation (LLOQ) of 15 IU/mL.

The ABBOTT Amplification Reagent Real Time kit HCV has a lower limit of quantitation and detection of 12 IU/mL.

### **2.8.3 Definition of Efficacy Endpoints**

Efficacy will be defined at different timepoints during the trial. Specific endpoints are:

- a) SVR4 (Sustained Virologic Response 4 weeks after the end of all study therapy). The subject has HCV RNA <LLOQ [either TD(u) or TND] 4 weeks after the end of all study therapy
- b) SVR12 (Sustained Virologic Response 12 weeks after the end of all study therapy): The subject has HCV RNA <LLOQ [either TD(u) or TND] 12 weeks after the end of all study therapy.
- c) SVR24 (Sustained Virologic Response 24 weeks after the end of all study therapy). The subject has HCV RNA <LLOQ [either TD(u) or TND] 24 weeks after the end of all study therapy.

### **2.8.4 Definition of Virologic Failure: Futility, Virologic Breakthrough, Rebound, and Relapse**

Lack of efficacy at different timepoints in the trial will be categorized as:

- Futility:

Subject has HCV RNA LLOQ [TD(q)] at treatment Week 4 with confirmation. The results of the next available blood draw will be used as the confirmatory test. This confirmatory test must be obtained within 2 weeks. Futility is defined as HCV RNA  $\geq 25$  IU/mL from the confirmatory test.

- Rebound

Subject has a rebound defined as  $>1$  log10 increase in HCV RNA from nadir while on treatment and confirmed from a separate blood draw within 2 weeks.

- Virologic breakthrough:

Subject has a confirmed HCV RNA  $\geq$  LLOQ [TD(q)] after being  $< 25$  IU/mL previously [TD(u) or TND]. Confirmation is defined as an HCV RNA  $\geq$  LLoQ from a separate blood draw repeated within 2 weeks.

- Relapse:

Subject has a confirmed HCV RNA  $\geq$  LLoQ [TD(q)] following end of all study therapy, after becoming undetectable (TND) at end of treatment. Confirmation is defined as an HCV RNA  $\geq$  LLoQ from a separate blood draw repeated within 2 weeks.

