## 2.4 Efficacy measurement

Sustained virologic response was the primary endpoint in all trials and was defined as HCV RNA less than the lower limit of quantification (LLOQ) at 12 weeks after the cessation of treatment (SVR). Serum HCV RNA values were measured during these clinical trials using the COBAS AmpliPrep/COBAS Taqman HCV test (version 2.0) with an LLOQ of 15 HCV RNA IU/mL, with the exception of Protocol 035/C-WORTHY and Protocol 047/C-SCAPE where the assay had an LLOQ of 25 HCV RNA IU/mL.

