## METHODS

Figure 1. Study design.

EBR = elbasvir; FW = follow-up week; GZR = grazoprevir; RBV = ribavirin; TW = treatment week.

- Phase 2, randomized, open-label study
  - Randomized treatment with GZR/EBR, with or without RBV
- Treatment-naive patients with GT1b infection
  - Cirrhotic and HIV-coinfected patients excluded
- Primary end point
  - SVR12 (HCV RNA <25 IU/mL)\* at follow-up week 12

\*COBAS TeqMan v2.0 (limit of quantitation [LOQ] = 25 IU/mL)

[figure not shown]

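### The breakthrough rule's prior-value cut-off of 25 IU/mL is the LLOQ of neither assay in this trial and does not match the bracket beside it

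*Combined protocol and SAP*

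**What the plan says.** The combined protocol and SAP permits two HCV RNA assays. Under section 2.8.2 the Roche test "has a lower limit of detection and quantitation (LLOQ) of 15 IU/mL", and "The ABBOTT Amplification Reagent Real Time kit HCV has a lower limit of quantitation and detection of 12 IU/mL". Section 8.1.3 repeats both limits.

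Section 2.8.3 ties the bracketed states to the assay limit. For SVR12: "The subject has HCV RNA <LLOQ [either TD(u) or TND] 12 weeks after the end of all study therapy". The SVR4 and SVR24 definitions have the same form.

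In section 2.8.4, breakthrough is a confirmed value at or above "LLOQ [TD(q)] after being $< 25$ IU/mL previously [TD(u) or TND"]. Confirmation is again at or above the LLOQ, "from a separate blood draw repeated within 2 weeks". The futility rule in the same section also uses 25, but as a stand-alone cut-off: a repeat of at least 25 "IU/mL from the confirmatory test".

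Elsewhere 25 IU/mL appears as an assay limit only for earlier trials. Section 2.4 names two studies "where the assay had an LLOQ of 25 HCV RNA IU/mL", and the Methods of the study in Annexe 1 give "limit of quantitation [LOQ] = 25 IU/mL". No text presents 25 as a deliberate common cut-off for the two assays used here.

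**The concern.** In sections 2.8.3 and 2.8.4 the bracket normally restates the numerical condition beside it: below LLOQ goes with TD(u) or TND, and at or above LLOQ goes with TD(q). In the breakthrough rule it does not. The number admits low quantifiable values that the bracket excludes. Because the event itself is set at the assay's own LLOQ, one value, such as 20 IU/mL on the Roche assay, can meet both the before and the after condition under the number.

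This rule decides treatment as well as classification. Sections 4.1 and 5.4 require treatment to stop when a virologic failure criterion is met, and section 5.4 makes the stop permanent. The proportion with virologic failure is a secondary endpoint (section 6.1.2). Two sites could read the same sentence differently. One would stop and count a patient whom the other would keep on treatment, in a trial that asks whether 8 weeks is long enough.

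**Working it through.** This is mainly a check of definitions. The plan has no figure of its own to reproduce.

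**Inputs.** LLOQ 15 and 12 IU/mL (2.8.2, 8.1.3); TD(u) or TND means below LLOQ (2.8.3); prior value below 25, event and confirmation at or above LLOQ, repeat within 2 weeks (2.8.4); on-treatment RNA at weeks 2, 4 and 8 (section 7); week 4 window +3 days (8.1.5.2.3); 56 daily doses; n = 120 and expected SVR12 of 96% (10.1).

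**Step 1: where number and bracket disagree (whole IU/mL).**

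| Assay | Bracket met | Number met | Disagreement | Width |
|---|---|---|---|---|
| Roche | < 15 | < 25 | 15 to 24 | log10(24/15) = 0.20 |
| Abbott | < 12 | < 25 | 12 to 24 | log10(24/12) = 0.30 |

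Below the LLOQ, and at 25 or above, the two conditions agree.

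**Step 2: a patient in the band.** Roche assay: 22 at week 2, 17 at week 4, 16 on repeat.

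- Breakthrough by the number: 22 < 25, and 17 and 16 are both ≥ 15. Yes.
- Breakthrough by the bracket: 22 < 15 is false. No.
- Futility: 16 ≥ 25 is false. No.
- Rebound: needs a rise of more than 1 log10 from nadir, and there is no rise. No.

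Under the number, the breakthrough rule stops a patient whom the futility rule would keep on treatment.

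**Step 3: treatment lost if triggered at week 4.** By the visit, 28 to 31 doses have been taken. The repeat comes 1 to 14 days later, and the stop is assumed to fall on that day.

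- Earliest stop: 28 + 1 = 29 doses; lost 56 − 29 = 27 (27/56 = 48%).
- Latest stop: 31 + 14 = 45 doses; lost 56 − 45 = 11 (11/56 = 20%).

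If the stop waits for the result, the loss is smaller.

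**Step 4: effect on the secondary endpoint.** One patient is 1/120 = 0.83 percentage points. For scale, assume 5 true failures (4% of 120 = 4.8), or 5/120 = 4.2%. One, two or three mislabelled patients who would not otherwise have failed give 6/120 = 5.0%, 7/120 = 5.8% or 8/120 = 6.7%. These counts are illustrative; the documents give no frequency. The study in Annexe 1 had no breakthrough or rebound in 61 patients (30 + 31), but with a quantitation limit of 25 it cannot show how often values fall in this band.

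**Step 5: does the corrected rule still work?** With the prior value below LLOQ, no value meets both conditions. A true breakthrough such as TND, then 40, then 60 is still caught at either LLOQ.

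**The case against.** The strongest reply is that the bracket already governs. If both conditions must hold, 22 IU/mL on the Roche assay is a quantified value, fails the bracket and is not breakthrough; the 25 is then merely redundant. That reading is available, and the sentence is not a logical contradiction. But the text does not state it, and the neighbouring definitions use the bracket to restate the number. If 25 was meant as a common cut-off instead, the bracket is wrong. The sentence needs correcting on either reading. (The abbreviation list in the text available for this review ends at LLoQ, so the meaning of TD(u) and TND is taken from section 2.8.3.)

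The reach is also narrow, and this stands. Taking the week 4 futility trigger as at or above LLOQ, a patient whose repeat is 25 or more is stopped anyway. The number therefore adds a week 4 stop only when the earlier value lies in the band, week 4 is still quantifiable, and the repeat is at or above LLOQ but below 25. At week 8 only the label can change. The 48% dose loss needs a repeat the day after the visit and a stop that same day. SVR12 is defined by the LLOQ, and section 10.4 treats most secondary analyses as exploratory.

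A last objection is that the proposed change leaves 25 in the futility rule. There, 25 is a free-standing confirmatory cut-off with no bracket to conflict with, so that rule can be applied as written.

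**Conclusion.** The concern holds as a minor defect. The prior-value threshold matches neither assay's LLOQ and disagrees with its own bracket over 15 to 24 IU/mL (Roche) or 12 to 24 IU/mL (Abbott). Confidence in the mismatch is high. Its practical effect depends on a site following the number, and on how many patients have values in the band, which the documents do not give and which is probably few. For such a patient at week 4 the consequence is a permanent stop with 20 to 48% of doses lost, assuming the stop is on the day of the repeat draw, and 0.83 percentage points on the virologic-failure proportion. Any effect on SVR12 is indirect, through shortened treatment. The sample size is unaffected.

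**What to change.** In the breakthrough definition in section 2.8.4, replace the prior-value phrase with: *< LLOQ of the assay used [TD(u) or TND] previously*. Number and bracket then coincide for both assays. Leave the SVR definitions at each assay's own LLOQ and leave the futility threshold unchanged.

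The cost is one phrase and a note to sites. Because it alters an evaluation criterion, it may need notifying to the ethics committee under section 13.3. It needs no new data, visits or patients.

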## 6. STUDY METHODOLOGY

### 6.1 Entry Criteria

#### 6.1.1 Primary endpoint

The primary efficacy endpoint is the proportion of subjects with SVR12 (HCV RNA < LLOQ 12 weeks after cessation of treatment) in the full analysis set

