#### 6.1.2 Secondary Endpoint

The secondary objectives of this study are as follows:

- To determine the proportion of subjects who attain SVR at 4 and 24 weeks after cessation of treatment (SVR4 and SVR24)
- To evaluate the proportion of subjects with virologic failure

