#### **8.1.5.3.2 Post Treatment Week 12 and 24 (+ 5 days)**

The following procedures are to be completed 12 and 24 weeks after taking the last dose of study drugs :

- Obtain body weight
- Obtain vital signs
- Assessment of AEs only related to study procedure
- Concomitant medications
- Obtain blood samples for :  
HCV RNA
- Confirmation of birth control
- Obtain urine sample for :  
Beta-HCG pregnancy test for females of childbearing potential only

Subjects with HCV RNA < LLOQ at the post treatment Week 12 Visit will return for the Post treatment Week 24 Visit

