### **10.3 Analyses for the primary outcome**

To evaluate the efficacy of Elbasvir/Grazoprevir Fixed-Dose Combination for 8 Weeks in Treatment-Naïve for HCV GT1b-Infected Patients, with non-severe fibrosis as measured by the proportion of subjects with sustained viral response 12 weeks after cessation of treatment (SVR 12), the proportion of patients presenting a sustained viral response 12 weeks after cessation of treatment (HCV RNA < LLOQ 12 weeks after cessation of treatment) will be presented with the associated 95% confidence interval estimated using binomial exact distribution (exact confidence interval). The lower-bound of the confidence intervals will be studied and analyzed regardless assumptions proposed for sample size estimation.

A detailed description of patients not assume SVR12 will be proposed according to clinical relevance using age, gender, BMI, fibrosis score, viral charge and additional endpoints as necessary

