### **10.4 Analyses for the secondary objectives**

Most of secondary analyses will be exploratory and will be performed as described previously (i) to evaluate the safety and tolerability of EBR/GZR treatment, (ii) to determine the proportion of subjects who attain SVR at 4 and 24 weeks after cessation of treatment (SVR4 and SVR24), (iii) to evaluate the proportion of subjects with virological failure and (iv) to evaluate the emergence of viral resistance to EBR/GZR during treatment and after cessation of treatment. Finally, to evaluate the kinetics of circulating HCV RNA during treatment and after cessation of treatment, a descriptive statistical analysis will be proposed. This analysis will be completed using random-effects models useful to evaluate kinetics taking into account between and within patient variability.

To better understand the potential for Resistance Associated Variants (RAVs) with EBR and/or GZR, samples will be retained from Day 1 and viral failure visits and RAVs will be assessed for any subject who has detectable virus above 1000 UI/mL and has met a virologic failure criteria. Subjects who discontinue the treatment will continue to participate in the scheduled follow-up activities including monitoring for resistance.

Exploratory IL28B genotyping may also be conducted to detect genetic variations associated with response to treatment of hepatitis C. A separate signature will be required to document a subject's agreement to provide additional samples for optional genetic research.

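### A post-treatment positive HCV RNA that is not repeated within 2 weeks, or that follows only TD(u) at end of treatment, fails SVR12 but is not a relapse, so it drops out of the virologic-failure proportion and of resistance testing

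*Combined protocol and SAP*

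**What the plan says.** Section 2.8.3 defines the primary endpoint by a single condition: "The subject has HCV RNA <LLOQ [either TD(u) or TND] 12 weeks after the end of all study therapy". Section 6.1.1 restates it ("HCV RNA < LLOQ 12 weeks after cessation of treatment"), and 10.3 analyses it with an exact binomial interval. None of these sections mentions a repeat sample.

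Section 2.8.4 attaches two further conditions to relapse. The positive value must be confirmed by another value at or above the LLOQ "from a separate blood draw repeated within 2 weeks", and it must come "after becoming undetectable (TND) at end of treatment".

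The failure definitions are then used elsewhere:

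- Section 6.1.2 lists as a secondary aim "To evaluate the proportion of subjects with virologic failure".
- Section 10.4 assesses resistance-associated variants (RAVs) only in a subject who has virus above 1000 IU/mL and who "has met a virologic failure criteria".
- Section 8.1.5.3.2 limits the last visit: "Subjects with HCV RNA < LLOQ at the post treatment Week 12 Visit will return for the Post treatment Week 24 Visit".
- Section 10.2 treats a missing categorical efficacy value as a failure unless it lies between two successes.

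**The concern.** One laboratory result is judged by two rules, and the plan does not say how to class a subject who meets one and not the other. In a single-arm trial of a shortened course, relapse is the expected way to fail. In the 8-week ribavirin-free group of the study in Annexe 1, both failures among 31 subjects were relapses, one found at follow-up week 12, with no breakthrough or rebound.

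If a real relapse goes unlabelled because a repeat draw was late or never made, the virologic-failure proportion is too low. The subject most informative about resistance may also not be tested. Section 4.1 refers to the same definitions when it allows the study to be terminated for an unacceptable rate of virologic failure, so the count is used for more than description.

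**Working it through.** **Step 1. Apply both rules to a week-12 value at or above the LLOQ.**

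| Repeat draw | End of treatment | SVR12 (2.8.3) | Relapse (2.8.4) |
|---|---|---|---|
| ≥LLOQ within 2 weeks | TND | Failure | Yes |
| ≥LLOQ within 2 weeks | TD(u) only | Failure | No |
| None, or later than 2 weeks | Any | Failure | No |
| <LLOQ | Any | Failure | No |

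Every discordant row is SVR12 failure without relapse. The opposite pattern, SVR12 success with virologic failure, needs a week-12 value below the LLOQ. An example is a relapse first seen at week 24. That comes from timing and not from the repeat rule.

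**Step 2. See whether another failure category picks these subjects up.** Futility concerns treatment week 4, and rebound is defined on treatment. Breakthrough needs the same confirmation within 2 weeks, so it cannot catch an unrepeated positive. Its definition does not say that it is limited to the treatment period, but footnote 6 of the flow chart names breakthrough and rebound as failure during therapy. On that reading a TD(u) subject with a confirmed post-treatment positive has no category.

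Scheduled visits do not supply the confirmation either. Follow-up weeks 4 and 12 are 8 weeks apart, so a subject positive at both is still unconfirmed without an extra draw.

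**Step 3. Follow the consequences.**

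- Unrepeated positive, or confirmed positive after TD(u): no virologic-failure criterion is met. The subject is not in the 6.1.2 numerator and does not qualify for RAV assessment under 10.4, even with a viral load far above 1000 IU/mL.
- Positive with a repeat below the LLOQ: calling this no relapse is reasonable. But 8.1.5.3.2 does not bring the subject back at week 24. The missing week-24 value has no success after it, so 10.2 makes SVR24 a failure by imputation.

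**Step 4. Size.** Inputs from 10.1: n = 120 and assumed SVR12 of 96%.

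- Expected failures: 120 × (1 − 0.96) = 4.8, about 5.
- One subject: 1/120 = 0.83 percentage points.

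| Subjects lost from the numerator | Reported virologic failure |
|---|---|
| 0 | 5/120 = 4.2% |
| 1 | 4/120 = 3.3% |
| 2 | 3/120 = 2.5% |

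This takes all 5 failures as virologic. The documents give no rate of missed or late repeats, so the rows show a range and not a forecast.

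**Step 5. The primary endpoint.** The exact two-sided 95% lower bound is the 0.025 quantile of Beta(x, n − x + 1). For x = 116 of 120 it is 91.7%, and for x = 115 it is 90.5%. The assumed 96% corresponds to 0.96 × 120 = 115.2 responders.

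**The case against.** The two endpoints are not meant to coincide. SVR12 is a responder proportion in which most missing values count as failures, while 2.8.4 sorts failures into confirmed types. Some non-responders without a confirmed virologic failure are to be expected. The flow chart has a column for a viral-failure confirmation visit with HCV RNA, so sites may obtain every repeat. Section 10.3 also promises a detailed description of subjects without SVR12, including viral load, where an unrepeated positive could be seen among about 5 cases. All of this stands, and it limits the size of the problem. It does not put the subject back into the 6.1.2 proportion or satisfy the 10.4 trigger, and a TD(u) subject is excluded from relapse even when every visit is kept.

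A reader might infer three stronger claims that the documents do not support:

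- *The endpoints disagree in both directions.* Step 1 shows one direction only.
- *An unconfirmed positive could carry the primary result across 91.5%.* Moving from 116 to 115 responders does so, but any single subject would. The design's own expectation rounds to 115, whose bound is already below 91.5%, and 10.3 ties no decision to that figure. Whether 120 subjects deliver the stated bound is a separate sample-size question.
- *The repeat should therefore decide SVR12.* Only positives would be retested, so SVR12 could only rise, in an open-label single-arm trial. A repeat up to 2 weeks later would also fall outside the +5-day window of the week-12 visit. That SVR12 rests on one value is itself read from silence, but it is the natural reading and the conservative one.

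**Conclusion.** The point holds for the secondary endpoint and the resistance analysis. Followed as written, 2.8.4 and 10.4 leave out a subject with a high post-treatment viral load if no timely repeat was drawn, and 2.8.4 does not class as relapse a confirmed positive after TD(u) at end of treatment. Each such subject lowers the reported virologic failure by 0.8 percentage points from about 4.2%, and one fewer of about 5 failures qualifies for RAV assessment.

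The size rests on the assumed 96% SVR12 and on all failures being virologic. The number of affected subjects is unknown and may be zero. The TD(u) route also rests on reading breakthrough as an on-treatment category. The unrepeated-positive route does not depend on that reading. The primary endpoint definition does not need to change.

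**What to change.** - **2.8.3:** keep SVR12 on the week-12 value, and say so explicitly.
- **2.8.4:** class a post-treatment value at or above the LLOQ as relapse unless a repeat draw is below the LLOQ. Count an unrepeated positive as failure. Accept any later post-treatment value at or above the LLOQ as confirmation. Replace the TND condition at end of treatment with <LLOQ. State whether breakthrough is limited to the treatment period, so that the categories do not overlap.
- **10.4:** retain the first positive sample above 1000 IU/mL and assess RAVs on it without requiring a timely repeat.
- **8.1.5.3:** keep a subject whose week-12 positive is not confirmed on repeat in follow-up to the week-24 visit, so that SVR24 is observed and not imputed.
- **Analysis:** report SVR12 with unconfirmed positives reclassified by their repeat value as a sensitivity analysis only.

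The cost is wording in these sections, storage of a sample already drawn, and an occasional week-24 visit. Relapse occurs after therapy, so redefining it does not alter when treatment is stopped. The one downside is that a few unrepeated low positives may be counted as virologic failures. List them separately so that the reader can see their effect.
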